6.4 Deaths and other Serious Adverse Events

Deaths and other serious adverse events (SAEs) will be tabulated following the same pattern than AEs. In addition, all deaths within 60 days from the first dose of treatment or within 30 days from the last dose of treatment will be listed.

7 OTHER ANALYSES

Descriptive statistics (mean, median, standard deviation, range of value, frequencies and percentages) will be used to summarize the data. Counts and percentages will be used for categorical variables, and summary tables will be used for continuous variables.

7.1 Baseline and Demographics

Descriptive statistics will be used to summarize the patients' baseline characteristics

Baseline data such as demographics, cancer history, prior therapy, prior relevant history, signs and symptoms, ECG, LVEF, physical examination, vital signs, laboratory values and concomitant medication, coded according to the World Health Organization (WHO) Anatomical Therapeutic Chemical (ATC) classification system, will be described following standard tables (detailed in Section 10, Appendix I).

Age, baseline weight, height and BSA values will be summarized descriptively. Age categories, sex, race and baseline ECOG PS will be summarized with frequency counts.

For the cancer history, times from initial diagnosis, metastatic disease, from locally advanced disease and from last progression before the study entry will be summarized. These time calculations will be shown in months and summarized descriptively. Histology and characteristics of the disease at study entry will be tabulated.

Previous relevant medical history (other than cancer) will be listed.

A frequency tabulation of the number of patients with the different types of previous surgery, radiotherapy or therapy will be given.

Signs and symptoms will be displayed by tabulation of frequencies according to NCI-CTCAE v.5 toxicity grades. Signs and symptoms will be listed.

In case of pre-treatment characteristics with multiple measurements per subject before the start of treatment (e.g. laboratory assessments or vital signs), the last value prior to or on the first day of treatment will be considered the baseline measurement.

7.2 Patient Disposition and Treatment/Study Discontinuation

The number of patients included and treated in the study will be shown. Also, accrual by center and the main dates of the study will be displayed. Reasons for treatment discontinuation and for study discontinuation will be tabulated.

7.3 Protocol Deviations

Analysis of inclusion/exclusion criteria deviations, retreatment restrictions, concomitant medication and clinically relevant discontinuations, among others, will be done as described in Appendix I.

7.4 Treatment Administration

Exposure to treatment will be described by treatment group.

Total cumulative dose, time on treatment, dose intensity and relative dose intensity, administration delay and dose reductions/omissions will be described following standard tables (detailed in Section 11, Appendix II). The reported cycle information on the case report form (CRF) pages will be used for the analysis.

Time on treatment, expressed in weeks, is defined as the last administration date of lurbinecetin minus the first administration date plus 31 days, except if the patient dies or starts a new antitumor therapy within 31 days from the last administration date, in which case the time on treatment will be the date of death or the start date of the new antitumor therapy minus the date of the first administration of the study treatment.

Total cumulative dose by drug, expressed in mg for both lurbinecetin and bosentan, is the sum of all the product doses received during the study, including the dose received in the last cycle.

For lurbinecetin, intended dose intensity is the planned dose per cycle divided by the planned number of weeks by cycle.

Absolute dose intensity is the actual cumulative dose divided by the number of weeks of treatment. As a convention, for this calculation, the duration of the last cycle will be the predefined cycle length (e.g. 21 days). Relative dose intensity (%) is the ratio of absolute dose intensity divided by the intended dose intensity.

The items « Infusion delayed: yes/no» and « Dose reduced: yes/no» present on the treatment exposure CRF pages will be used to calculate delays and dose reductions, respectively. For cycles considered as delayed by the Investigator, the length of the delay will be calculated as:

Duration of cycle delay: Date of the current drug administration – Date of the previous drug administration – the predefined cycle length (i.e., 21 days).

If the number of delays or dose reductions are very low, tables will not be presented and only listings will be shown.

7.5 *Subsequent Therapies*

A listing of subsequent therapies received after treatment discontinuation will be shown by total and treatment sequence group.

7.6 *Subgroup Analyses*

Safety analysis will be done by sequence (Sequence 1 [TR] vs Sequence 2 [RT]) and treatment group (Test [lurbinectedin administered in combination with bosentan] vs Reference [lurbinectedin alone]). Additional groups could be done (such a dose level in case dose of lurbinectedin was adjusted) if required, and a sequential number will be added at the end of the table number to differentiate them within each section.

No other subgroup analysis is planned.

7.7 *Pharmacogenetics Analyses*

The analysis will be detailed and reported in a separate document.

7.8 *Decimal places*

By default, all results will be rounded to one decimal, except when variables are integers; in that case, they will be reported without decimals, (e.g. age in years or number of sites).

7.9 *Imputation in Incomplete Dates*

The dates of certain historical or current clinical activities are key component for statistical analysis. An incomplete date results from a missing day, month or year; in that case, the missing figure can be imputed allowing for the calculation of variables, such duration and time to certain event. However, when all of them, day, month and year, are missing no imputation will be done.

Before randomization/treatment start date

All variables needed to summarize for example prior information (e.g. first diagnosis date) where partial information is available will be subject of imputation by means of SAS programming. If the day of a date is unknown then the imputed day will be 1, if the month is also unknown then the imputed date will 1/July. This assumption will be valid if the imputed date is earlier than the randomization date; otherwise, the imputed date will be the first day of the month of the randomization date (i.e. 01/Randomization month date/year).

Between treatment start and end of treatment

All date variables during treatment where information is needed and is not fully available, for example adverse events or concomitant medications, will be subject of imputation by means of SAS programming. If the day of a date is unknown then the imputed day will be 1, if the month and/or year is also unknown then the imputed date will be 1/January (this assumption will be valid if the imputed date is not earlier than the treatment start date; otherwise, the imputed date will be the treatment start date).

After end of treatment

A conservative approach for the variables collecting information after end of treatment where partial information is available (e.g., follow-up AEs) will be imputed by means of SAS programming. The following rules will be implemented: if the day of a date is unknown then the imputed day will be 1; if the month is also unknown, then the imputed date will be 1/July. This assumption will be valid if the imputed date occurs later than the last drug administration date; otherwise, the imputed date will be the last study drug administration date plus 1 day.

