5.2 PLANNED STUDY PERIODS (INDIVIDUALLY PER PATIENT)

Patients will be evaluated at scheduled visits in three study periods:

- **Pre-treatment (screening)**: from signature of the ICF to the day of first administration of the study treatment (bosentan or lorbinectedin).
- **Treatment**: from first administration of the study treatment (bosentan or lorbinectedin) to the last dose of lorbinectedin plus 31 days (end-of-treatment, EOT) (maximum of three cycles).
- **Follow-up of adverse events**: after EOT, patients with treatment-related toxicities $>$ grade 2 will be followed every four weeks until recovery to at least grade 1 or stabilization of all treatment-emergent AEs, or until the start of a new antitumor therapy, until the continuation of treatment outside this study under a Compassionate Use Agreement or death, whichever occurs first.

Patients will be considered to be **on-study** from the signature of the ICF to the end of the follow-up period. Patients will be considered to be **on-treatment** for the duration of their treatment and until the day of EOT, immediately before the start of the follow-up period.

An end-of-treatment visit will be performed within 31 days (± 10 days) after administration of the last dose of lorbinectedin, unless the patient dies or starts any new antitumor therapy outside this clinical study, in which case the EOT visit should be performed immediately before the start of the new therapy (ideally the day before or the same day).

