5.2.1 Discontinuations

5.2.1.1 Treatment Discontinuation

Treatment discontinuation occurs when an enrolled patient ceases to receive the study treatment regardless of the circumstances. By convention, the date of EOT is defined as 31 days after the day of the last dose of lorbinectedin (treatment discontinuation), the start of a new antitumor therapy or death, whichever occurs first, in which case the date of administration of this new therapy or the date of death will be considered the date of EOT.

The primary reason for any treatment discontinuation will be recorded on the patient's electronic Case Report Form (eCRF).

If a patient discontinues treatment, every effort should be made to complete the scheduled assessments as appropriate.

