9.3.2 Safety

All AEs will be graded according to NCI-CTCAE v.5.

Treatment-emergent adverse events (TEAEs) are any adverse event aggravated in severity from baseline or having their onset between the first dose of the study drug and 31-day (± 10 days) after the last treatment dose, death or date of further therapy, whichever came first. AEs related to the study treatment or with unknown relationship occurring more than 31 days after the last dose were also taken into account as TEAEs.

Descriptive statistics will be used to characterize the profiles of drug-related AEs, drug-related deaths, SAEs, clinical laboratory data, drug-related delays and/or treatment discontinuations. Tables will be displayed by sequence and treatment (Test or Reference).

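### SAP 7.9 sets a missing day to the first of the month for every post-treatment date; for the start of new antitumor therapy this shortens the treatment-emergent window and time on treatment

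*SAP*

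**What the plan says.** The last part of SAP 7.9 covers dates after end of treatment. It begins "A conservative approach for the variables collecting information after end of treatment where partial information is available (e.g., follow-up AEs", the bracket closing there, so follow-up AEs are its only example. Then "if the day of a date is unknown then the imputed day will be 1", and "if the month is also unknown, then the imputed date will be 1/July". If the result does not fall after the last administration, "otherwise, the imputed date will be the last study drug administration date plus 1 day". There is no separate rule for a date that closes a window.

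The start of further antitumor therapy is collected as a follow-up variable (SAP Listing 13.37), so the rule covers it. That date closes three periods:

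- **Treatment-emergent window.** Protocol 9.3.2 ends it 31 days after the last dose, or at "death or date of further therapy, whichever came first".
- **EOT date.** In protocol 5.2.1.1, "the date of EOT is defined as 31 days after the day of the last dose", with new therapy or death replacing that date if earlier.
- **Time on treatment.** In SAP 7.4, if death or new therapy comes within 31 days of the last administration, "the time on treatment will be the date of death or the start date of the new antitumor therapy", minus the first administration date.

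**The concern.** Moving a date early has opposite effects depending on what the date does. An AE onset moved early stays inside the window, so more events count. A window-closing date moved early leaves fewer days in the window, so fewer events count. The SAP gives both the same treatment and the same label.

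The affected events would already be in the database, because protocol 8.5.1 collects AEs until new therapy actually starts. SAP section 6 bases the safety analysis on treatment-emergent AEs and SAEs. An event between the imputed and the true start can therefore be collected and then left out of the AE and SAE tables. The protocol 9.3.2 exception does not bring it back: it covers only related or unknown-relationship events more than 31 days after the last dose. Time on treatment (SAP Table 11.1.1.2) is understated through the same date.

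**Working it through.** The plan gives no figure to reproduce, so the check applies the stated rule to enumerated dates.

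**Rule, day missing.** Let L be the last dose and S the true start of new therapy.

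- Imputed start I = first of the month of S if that is after L, otherwise L + 1 day.
- Window length = min(31, start − L).
- Days lost = min(31, S − L) − min(31, I − L).

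The first of a month is never later than any day in it, and L + 1 is never later than a start after L. So I ≤ S, and the loss is never negative.

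**Hand examples, last dose 10 March.**

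| Recorded | True start | Imputed (SAP) | True window | SAP window | Window with month-end date |
|---|---|---|---|---|---|
| March | 30 March | 11 March (floor) | 20 days | 1 day | 21 days |
| April | 8 April | 1 April | 29 days | 22 days | 31 days (cap) |
| April | 25 April | 1 April | 31 days | 22 days | 31 days (cap) |

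In the third row no cut is due, but the imputed date creates one.

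**Enumeration at fixed start days.** All 730 last-dose dates in 2021–2022 are used, with the day missing. Means are over all 730 dates, including those not shortened. The last column repeats the calculation with the last day of the month of S in place of I.

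| True start | True window | Mean days lost (SAP) | Imputed to L + 1 | Imputed to day 10 or earlier | Mean days added (month-end) |
|---|---|---|---|---|---|
| Day 21 | 21 days | 13.1 | 34% | 64% | 8.2 |
| Day 28 | 28 days | 14.6 | 11% | 41% | 2.8 |
| Day 35 | 31 days | 11.0 (84% shortened) | 0% | 18% | 0 |

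**Enumeration over a range of starts.** For 365 last-dose dates in one year and true starts on days 1 to 31, there are 365 × 31 = 11,315 pairs:

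- The imputed date is later than the true date in none.
- The window is shortened in 93.6%, by a mean of 9.7 days over all pairs (median 8, maximum 30), against a mean true window of 16 days.
- In 47% new therapy starts in the same month as the last dose, and the floor leaves a 1-day window.

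For true starts on days 32 to 61 (365 × 30 = 10,950 pairs) the full 31 days should apply, yet the window is cut in 46%, by up to 29 days.

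**Month also missing.** Under the 1 July rule and true starts on days 1 to 31, the window is too short in 49% of pairs, too long in 48% and unchanged in 3%. There is no consistent direction.

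All percentages assume that a partial date exists and that last-dose dates are spread evenly over the calendar. The ±10-day tolerance around day 31 is ignored.

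**The case against.** The strongest reply is that the trigger is rare. Protocol 5.2 places the EOT visit just ahead of new therapy ("in which case the EOT visit should be performed immediately before the start of the new therapy"), ideally the day before or the same day, so the site should normally know the date. SAP Listing 11.7.2.1 shows end of treatment beside the therapy start, where a mismatch would be visible. The documents give no frequency of partial dates. This stands, and it is the main reason the point is minor.

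The rule also suits its stated example, follow-up AEs, as regards onset. And the SAP does not itself state a cut at new therapy: the link runs through protocol 9.3.2, and the listings of grade ≥ 3 AEs, all SAEs and all AEs (11.2.1.8, 11.3.1.7, 13.29) mention no cut. Events would remain visible there. Both remarks are correct; neither makes the tables or time on treatment right.

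A reader might infer more than the documents support:

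- **That the windows can only shrink.** True for a missing day, not when the month is missing too.
- **That toxicity at the blood-count nadir is hidden.** Haematology and biochemistry tables come from laboratory values. SAP 6.2 maps EOT laboratory visits to the last cycle, and no passage cuts these tables at new therapy. Protocol 8.5.1 records abnormal laboratory results as AEs only under listed conditions.
- **That the bosentan cycle loses events selectively.** Cycle 2 of Sequence 1 and the optional Cycle 3 in both sequences are lurbinectedin alone, so the shortened cycle can be either treatment.
- **That early AE end dates distort results.** SAP Appendix II has no summary of AE duration that uses them.

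**Conclusion.** The point holds for one class of date. For the start of new antitumor therapy with only the day missing, the rule in SAP 7.9 cannot lengthen the treatment-emergent window or time on treatment and usually shortens them. The size, given such a date, is a mean loss of 13 days for a true start on day 21, 15 days for day 28, and 11 days for day 35, where none should be lost. The label conservative is right for AE onset and wrong here.

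The practical effect is small. It needs a partial new-therapy date soon after the last dose, and it touches descriptive AE and SAE tables, any AE comparison under SAP 11.5, and time on treatment. One such patient would be 1 of 8 (12.5%) if the safety population is the planned eight. The primary PK comparison and the laboratory-grade tables are not shown to be affected. Dose intensity is unaffected, because SAP 7.4 fixes the length of the last cycle. Severity: minor.

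**What to change.** In SAP 7.9:

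- Keep the early-date rule for AE onset.
- For the start of new antitumor therapy with a missing day, impute the last day of the known month, no earlier than the EOT visit actually performed and no later than death, off-study date or clinical cut-off.
- Treat a partial death date the same way where it closes the window.
- Do not use EOT date + 1 as a general floor: the EOT date can itself be set by the new-therapy date, so that floor would be circular. The date of the visit performed avoids this.
- State the treatment-emergent window in the SAP, so that the cut at further therapy does not rest on the protocol alone.

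The cost is a few lines of SAP text and code. The downside is an error in the other direction: time on treatment may be too long (before the bounds, by a mean of 8.2 days for a true start on day 21 and 2.8 days for day 28), and a few events after new therapy began may count as treatment-emergent. For a safety summary that is the direction the word conservative implies. The change does not address the 1 July rule for a missing month.

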7.10 Variable Unit Standardization

Variables reported with different units will be homogenized to standardized variables following the International System of Units (e.g. laboratory tests, biometrical assessments...) unless otherwise specified in the following sections.

7.11 Decimal Places, Missing Values and Allowed Assessment Windows

By default, all numeric results will be rounded to one decimal place, except when variables are integer, which will be reported without decimals (e.g., age in years, number of sites, etc.). Four decimals will be used for p-values.

Missing values will not be included in the calculation of percentages. Assessment windows as specified in the clinical protocol will be respected.

7.12 Identification of Fixed or Random Effects Models

Not applicable (NA).

8 STATISTICAL SOFTWARE

Medidata Rave® EDC will be used for data entry and clinical data management.

Medidata Rave® RTSM will be used for permuted block randomization design and management.

SAS® v.9.4 or superior will be used for all statistical analysis outputs.

10 APPENDIX I: PATIENTS DISPOSITION

10.1 General Characteristics

The general characteristics analysis will be carried out on the enrolled population.

10.1.1 Patient Disposition

Main characteristics concerning inclusion in the study, withdrawal from the study and protocol deviations will be displayed in this section.

Table 10.1.1.1 Patient accrual by institution

	S1 (TR)		S2 (RT)		Total	
	N	%	N	%	N	%
Institution 1						
Institution 2						
Total						

Notes: Percentage is based on number of patients in total and by sequence, when applicable.

S1, Sequence 1; S2, Sequence 2; TR, test-reference; RT, reference-test.

Table 10.1.1.2 Disposition of patients

Relevant study dates
Date of first consent
Date of first dose/first patient
Date of last consent
Date of first dose/last patient
Date of last dose
Date of last follow up*

(*): Last follow up date, examination date or procedure before study closure.

Table 10.1.1.3 Number of patients evaluable for analysis

	S1 (TR)		S2 (RT)		Total	
	N	%	N	%	N	%
Evaluable for Safety						

Notes: Percentage is based on number of patients in total and by sequence, when applicable.

S1, Sequence 1; S2, Sequence 2; TR, test-reference; RT, reference-test.

Listing 10.1.1.4 Non-evaluable patients

Not Evaluable for	Sequence	Subject	Reason(s)
Safety			
PK			

10.1.2 Treatment Discontinuations

Table 10.1.2.1 Treatment discontinuation

	S1 (TR)		S2 (RT)		Total	
	N	%	N	%	N	%
Protocol Treatment Completed						
Patient moved to Compassionate Use						
Progressive disease						
Adverse Events						
Patient refusal to treatment						
Investigator's decision						
Death						
Other						
Total						

Notes: Percentage is based on number of patients in total and by sequence, when applicable.

S1, Sequence 1; S2, Sequence 2; TR, test-reference; RT, reference-test.

Listing 10.1.2.2 Treatment discontinuation due to related[†] Adverse Events

Sequence	Subject	AE reported	Preferred term	Grade	Relationship	Serious Event

Notes: [†] Related or unknown relationship.

Listing 10.1.2.3 Treatment discontinuation due to non-related Adverse Events

Sequence	Subject	AE reported	Preferred term	Grade	Relationship	Serious Event

Listing 10.1.2.4 Reasons for treatment discontinuation other than Progressive Disease

Sequence	Subject	Reason	Specify

Table 10.1.2.5 Reasons for study discontinuation

	S1 (TR)		S2 (RT)		Total	
	N	%	N	%	N	%
Patient's follow-up completed						
Patient moved to Compassionate Use						
Study termination (clinical cut-off)						
Withdrawal of consent						
Death						
Never treated						
Lost to follow up						
Other						
Total						

Notes: Percentage is based on number of patients in total and by sequence, when applicable.
 S1, Sequence 1; S2, Sequence 2; TR, test-reference; RT, reference-test.

Listing 10.1.2.6 Reasons for study discontinuation due to other reason

Sequence	Subject	Other, specify

Listing 10.1.2.7 Patients never treated

Sequence	Subject	Reason

10.1.3 Protocol Deviations

Classification will be based on the following group categories:

- Inclusion/exclusion criteria not met
- Incorrect treatment, dose or schedule received
- Excluded concomitant medication received
- Withdrawal criteria met, but treatment continued
- Failure to comply study procedures
- Any other Ethical/GCP issues

Listing 10.1.3.1 Relevant protocol deviations

Sequence	Subject	Protocol deviation Type	Specify Deviation

